#### **Change in calcium excretion from baseline (SV2) to Week 4 in 24-hour urine**

The analysis of the 24-hour urinary calcium excretion data will be based on a subset of the safety analysis set including the subjects undergoing HPA axis testing. The analysis will be performed as outlined above for the analysis of the albumin-corrected serum calcium data.

In addition, calcium excretion at the 24-hour urine collection will also be presented separately for subjects with complete urinary collection. A 24-hour urinary collection is considered incomplete if it is either reported to be incomplete by the subject or if the creatinine excretion is below 0.1 mmol per kg body weight as proposed by Remer et al (29).

#### **Change in calcium:creatinine ratio from baseline (SV2) to Week 4 in 24-hour urine**

The analysis of the 24-hour urinary calcium:creatinine ratio data will be based on a subset of the safety analysis set including the subjects undergoing HPA axis testing. The analysis will be performed as outlined above for the analysis of the albumin-corrected serum calcium data.

### **11.3.5 Analysis of Secondary Endpoints**

#### **Subjects with serum cortisol concentration $\leq 18$ mcg/dl at both 30 and 60 minutes after ACTH-challenge at Week 4**

Subjects with a serum cortisol concentration  $\leq 18$  mcg/dl at both 30 and 60 minutes after ACTH-challenge at Week 4 will be analysed as described for subjects with a serum cortisol concentration  $\leq 18$  mcg/dl at 30 minutes after ACTH-challenge at Week 4 in section 11.3.4.

### Change in calcium:creatinine ratio from baseline (SV2) to Week 4 in spot urine

The analysis of the calcium:creatinine ratio in spot urine will be based on a subset of the safety analysis set including the subjects not undergoing HPA axis testing. The analysis will be performed as described for the analysis of the albumin-corrected serum calcium data in section [11.3.4](#).

### Subjects with ‘treatment success’ (i.e., ‘clear’ or ‘almost clear’ for subjects with at least ‘moderate’ disease at baseline, ‘clear’ for subjects with ‘mild’ disease at baseline) according to the physician’s global assessment of disease severity on the body at Week 4

The statistical analysis of efficacy will be based on the full analysis set. The percentage of subjects who achieve ‘treatment success’ according to the PGA on the body will be presented by visit and at end of treatment. The 95% CI, which is based on a binomial distribution, will be presented for the proportion of subjects with ‘treatment success’ at Week 4 and at end of treatment.

The percentage of subjects who achieve ‘treatment success’ according to the PGA on the body at Week 4 and at end of treatment will also be tabulated by age-group, sex, ethnicity, race, centre and baseline PGA on the body.

### Subjects with ‘treatment success’ (i.e., ‘clear’ or ‘almost clear’ for subjects with at least ‘moderate’ disease at baseline, ‘clear’ for subjects with ‘mild’ disease at baseline) according to the physician’s global assessment of disease severity on the scalp at Week 4

Subjects with ‘treatment success’ according to the PGA on the scalp will be analysed as outlined above for the body.

### Percentage change in PASI from baseline (V1) to Week 4

PASI is calculated using the formula given below based on the physician’s assessment of the extent and severity of the disease locally (head, trunk, arms, legs) [\(8.14\)](#).

The following formula will be used to calculate the PASI:

$$\text{Head } 0.1 (R + T + S)E = W$$

$$\text{Arms } 0.2 (R + T + S)E = X$$

$$\text{Trunk } 0.3 (R + T + S)E = Y$$

$$\text{Legs } 0.4 (R + T + S)E = Z$$

Where: R = score for redness; T = score for thickness; S = score for scaliness; E = score for extent

The sum of W + X + Y + Z gives the total PASI, which can range from 0 to 72.

The percentage change in PASI from baseline (V1) to each visit and to end of treatment will be summarised for the full analysis set. The 95% CI for mean percentage change in PASI based on a normal distribution will be calculated for Week 4 and for end of treatment.

**Subjects with ‘treatment success’ (i.e., ‘clear’ or ‘very mild) according to the subject’s global assessment of disease severity on the body at Week 4**

The percentage of subjects who achieve ‘treatment success’ according to the subject’s global assessment of disease severity on the body will be presented by visit and at end of treatment for the full analysis set. The 95% CI based on a binomial distribution will be calculated for the proportion of subjects with ‘treatment success’ at Week 4 and at end of treatment.

**Subjects with ‘treatment success’ (i.e., ‘clear’ or ‘very mild) according to the subject’s global assessment of disease severity on the scalp at Week 4**

Subjects with ‘treatment success’ according to the subject’s global assessment of disease severity on the scalp will be analysed as outlined above for the body.

**Change in itch as assessed by the VAS from baseline (V1) to Week 4**

The change in itch as assessed by the VAS from baseline (V1) to each visit and to end of treatment will be summarised for the full analysis set. The 95% CI for mean change in itch based on a normal distribution will be calculated for Week 4 and for end of treatment.

### **11.3.6 Exploratory Analysis of Efficacy**

The exploratory analysis of efficacy will be based on the full analysis set.

The PGA on the body and on the scalp, PASI and subject’s global assessment of disease severity on the body and on the scalp will be summarised by visit and at end of treatment.

The physician’s assessment of extent of psoriasis (total involvement as % of BSA , on trunks and/or limbs as % of BSA and on scalp as % of scalp area) will be summarised by visit and at end of treatment.

## 11.3.7 Analysis of Patient-Reported Outcomes

### Subject's assessment of itch

Subject's assessment of itch will be summarised by visit and at end of treatment for the full analysis set.

### Subject's assessment of itch-related sleep loss

Subject's assessment of itch-related sleep loss will be summarised by visit and at end of treatment for the full analysis set. In addition, the change from baseline to each visit and to end of treatment will be summarised.

### Children's Dermatology Life Quality Index

The CDLQI total score will be analysed as outlined above for subject's assessment of itch-related sleep loss.

Additionally, the percentage of subjects with CDLQI scores of 0 or 1 indicating no or minimal impact on quality of life will be presented by visit and at end of treatment including only the subjects with the baseline score of  $> 1$ .

Furthermore, the percentage of subjects with  $\geq 5$  points improvement in CDLQI score from baseline will be presented by visit and at end of treatment for the subjects with the baseline score  $\geq 5$ .

### The Family Dermatology Life Quality Index

The FDLQI total score will be analysed as outlined above for the CDLQI.

## 11.3.8 Analysis of Safety

The analysis of safety will be based on the safety analysis set, except where otherwise stated.

### 11.3.8.1 Adverse Events

Adverse events will be coded during the course of the trial according to MedDRA. Adverse events will be presented by preferred terms and primary system organ class.

Treatment emergent AEs will be summarised, however all adverse events recorded during the course of the trial will be included in the subject data listings. An event will be considered emergent with the trial treatment if started after the first application of investigational product or if started before the first application of investigational product (applicable if subject had a

wash-out) and worsened in severity thereafter. The tabulations described in the following will only include the events that are emergent with trial treatment. In each of the tabulations, adverse events are defined by MedDRA preferred terms within primary system organ class.

An overall summary of the number (percentage) of subjects with any treatment emergent AEs, SAEs, premature discontinuations from the trial due to AEs, treatment related AEs and severe AEs will be presented.

The number of subjects experiencing each type of adverse events will be tabulated regardless of the number of times each adverse event is reported by each subject.

The severity for each type of adverse event will be tabulated. Where there are several recordings of severity for a given type of adverse event, severity will be taken as the most severe recording for that adverse event.

The causal relationship to trial medication for each type of adverse events will be tabulated. Where there are several recordings of causal relationship to the investigational product for a given type of adverse event, causal relationship will be taken as the most-related recording from the last report of that adverse event, since that is when the (sub)investigator will be in possession of most information and so best able to judge causal relationship.

Related adverse events are defined as adverse events for which the (sub)investigator has not described the causal relationship to investigational product as 'not related'. The number of subjects experiencing each type of related adverse event will be tabulated regardless of the number of times each related adverse event is reported by each subject.

The number of subjects experiencing each type of lesional/perilesional adverse event, lesional/perilesional adverse event on the body and lesional/perilesional adverse event on the scalp will be tabulated.

Serious adverse events will be evaluated separately and a narrative for each will be given.

AEs leading to withdrawal from trial or discontinuation of investigational product will be listed.

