Table 3-49 Adverse events by MedDRA primary system organ class: safety analysis set

Table 3-50 Adverse events by MedDRA primary system organ class and preferred term: safety analysis set

Table 3-51 Severity of adverse events by MedDRA primary system organ class and preferred term: safety analysis set

Table 3-52 Causal relationship of adverse events to IMP by MedDRA primary system organ class and preferred term: safety analysis set

Table 3-53 Related adverse events by MedDRA primary system organ class and preferred term: safety analysis set

Table 3-54 Severity of adverse drug reactions by MedDRA primary system organ class and preferred term: safety analysis set

Table 3-55 Lesional/perilesional adverse events by MedDRA primary system organ class and preferred term: safety analysis set

Table 3-56 Lesional/perilesional adverse events on the body by MedDRA primary system organ class and preferred term: safety analysis set

Table 3-57 Lesional/perilesional adverse events on the scalp by MedDRA primary system organ class and preferred term: safety analysis set

Table 3-58 Adverse events by age group, MedDRA primary system organ class and preferred term: safety analysis set

Note: Only for subgroups.

Table 3-59 Adverse events by sex, MedDRA primary system organ class and preferred term: safety analysis set

Table 3-60 Adverse events by race, MedDRA primary system organ class and preferred term: safety analysis set

Trial ID: LP0053-1108	Date: 12-Jun-2018	Version: 1.0 Page 26 of 29
-----------------------	--------------------------	-------------------------------

Table 3-61 Adverse events by baseline PGA on the body, MedDRA primary system organ class and preferred term: safety analysis set

Table 3-62 Adverse events by baseline PGA on the scalp, MedDRA primary system organ class and preferred term: safety analysis set

Table 3-63 Adverse events by baseline total extent of body and scalp psoriasis, MedDRA primary system organ class and preferred term: safety analysis set

Table 3-64 Adverse events by IMP usage, MedDRA primary system organ class and preferred term: safety analysis set

Table 3-65 Local safety and tolerability by visit: safety analysis set

Note: Both number and percentage of subjects in each of the four categories ('Absent' to 'Severe').

Table 3-66 Systolic blood pressure by visit: safety analysis set

Table 3-67 Change in systolic blood pressure from baseline to each visit: safety analysis set

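### The causality table rates each preferred term by its last report only, so an earlier related event can be shown as 'not related' and Tables 3-52 and 3-53 can disagree

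*Protocol*

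**What the plan says.** Protocol section 11.3.8.1 first fixes the unit of analysis: "In each of the tabulations, adverse events are defined by MedDRA preferred terms within primary system organ class". It counts subjects with each term "regardless of the number of times each adverse event is reported by each subject".

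Two rules then reduce several ratings to one per subject and term:

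- **Severity:** "severity will be taken as the most severe recording for that adverse event".
- **Causality:** the rule is triggered by "Where there are several recordings of causal relationship to the investigational product for a given type of adverse event", and then "causal relationship will be taken as the most-related recording from the last report of that adverse event". The reason given is "since that is when the (sub)investigator will be in possession of most information and so best able to judge causal relationship".

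A separate paragraph defines related events as those whose relationship the investigator has not rated 'not related'. It gives them their own tabulation and does not mention the last report.

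SAP section 6.3.3 keeps the protocol's presentation of AEs and adds event counts beside subject counts. SAP Appendix I lists the causality table as Table 3-52, "Causal relationship of adverse events to IMP by MedDRA primary system organ class and preferred term", and the related-event table as Table 3-53. Neither entry restates or amends the rule.

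**The concern.** The reason given for the causality rule fits successive reports of one event: as follow-up accrues, the latest judgement is the best informed. It does not fit two separate events that share a preferred term. A later judgement about the second event says nothing about the cause of the first. Because the table's unit is the preferred term, the rule as worded covers both situations and discards the first event's rating in each.

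The trial's primary objective is safety and it has no comparator arm, so the investigator's causality rating is one of the main means of attributing events to the product. What is at stake is whether the causality table shows every subject who had a related event of a given term, and whether it agrees with the related-event table beside it.

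**Working it through.** **The plan's own AE figure.** Protocol section 11.1 gives a probability of at least 86.7% of seeing at least one case, for an event with true frequency 2% among 100 subjects. Check: 1 − 0.98^100 = 0.8674, which reproduces it. The point here does not depend on that figure; it concerns a rule.

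**Applying the rule.** Take two separate events of the same term in one subject, in time order. Order the ratings as in Protocol section 27.2: not related < possibly < probably.

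| First event | Later event | Rule as worded | Most-related over both | Any record not rated 'not related'? |
|---|---|---|---|---|
| probable | not related | not related | probable | yes |
| possible | not related | not related | possible | yes |
| probable | possible | possible | probable | yes |
| not related | possible | possible | possible | yes |

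In the first two rows the subject is entered as 'not related' in Table 3-52 despite a related event. In the third the attribution is weakened. In the fourth the two rules agree. The last report is one of the reports over which the maximum would be taken, so the worded rule can never give a more-related entry than the maximum.

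**Consequence for Table 3-53.** There are two ways to program it, and the documents do not say which applies:

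- From individual records: rows one and two count as related in Table 3-53 and as 'not related' in Table 3-52, for the same subject and term.
- From the causality already derived for Table 3-52: the tables agree, but the related case is missing from both.

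**What is not touched.** Protocol section 11.3.4 analyses the AE primary endpoint by how many subjects, and what percentage, had each type of event. Causality does not enter. Section 11.3.8.1 keeps all AEs in the listings, and SAP Listing 7-5 carries them.

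**Size.** One affected subject is 1/100 = 1.0 percentage point for that term at the planned size, or 1/106 = 0.94 of a point with the 106 treated subjects shown in SAP Table 2. The documents give no count of subjects with repeated terms and differing ratings.

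As an illustration only, assume k independent events of one term in a subject, each judged related with probability p. Among such subjects with at least one related event, the share shown as 'not related' is [1 − (1 − p)^k − p] / [1 − (1 − p)^k]:

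| | p = 0.2 | p = 0.5 | p = 0.8 |
|---|---|---|---|
| k = 2 | 0.16/0.36 = 44% | 0.25/0.75 = 33% | 0.16/0.96 = 17% |
| k = 3 | 0.288/0.488 = 59% | 0.375/0.875 = 43% | 0.192/0.992 = 19% |

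These are shares of subjects who already have repeated events of one term, not of the trial population. Ratings within a subject are unlikely to be independent, and positive dependence would lower the shares.

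**The case against.** The strongest reply is that the authors meant follow-up of a single event. Their stated reason makes sense only on that reading, and the sentence could be taken to mean: settle each event at its last report, then take the most-related. This stands as a probable intention. It does not rescue the wording. The trigger is the type of event, which the section defines by preferred term, and the section also speaks of one such event being reported several times by a subject. Appendix 3 of the protocol describes one causality category per AE, so asking for the most-related rating within the last report has a purpose only if that report can hold several records of the term. A programmer following the text would lose the earlier rating.

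Three further replies stand:

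- A reader might infer that the primary AE endpoint is biased. It is not, because its counts do not use causality.
- A reader might infer that related events are hidden from the report. The documents do not support that: the related-event definition has no last-report limit, and the listings keep every event. The SAP's added event counts may also help, although it does not say how events are assigned to causality categories.
- Recurrence with a lower rating inside a four-week, three-visit treatment period may be rare. Section 3.2.1 names application site irritation and pruritus as the most common effects in adults, but it also reports a low incidence of AEs and says nothing about recurrence.

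A worsening recorded as a new AE (section 27.1) is weak support for the separate-event case. There the later record continues the same condition, and preferring the later judgement is defensible.

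**Conclusion.** The point holds for the subject-level entries in Table 3-52 and for the consistency of that table with Table 3-53. As worded, the rule can show a subject with a related event as 'not related' for that term. Against the most-related rating over all events, it can only lower attribution. Whether Table 3-53 then disagrees or shares the loss depends on programming that the documents leave open.

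The size is about one percentage point per affected subject and term. The number of such subjects is unknown and may be zero. The conclusion rests on the literal reading of section 11.3.8.1, which the SAP does not change. This should be corrected because it is cheap and concerns attribution in a safety trial, but it does not threaten the primary analysis.

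**What to change.** State the rule in two ordered steps:

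1. For each individual AE record, use the investigator's latest causality rating.
2. For each subject and preferred term, tabulate the most-related rating across all treatment-emergent AE records of that term.

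Add that a worsening entered as a new AE counts as its own record in step 2. This settles the order of the two steps without needing a link between records. Derive Tables 3-52 and 3-53 from the same record-level ratings. The authors' reason for preferring the latest judgement is kept where it fits, in step 1, and step 2 matches the severity rule.

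**Cost.** No new data are needed; the change is a short SAP text and a small change to the derivation. Related counts in Table 3-52 can stay the same or rise, never fall. A worsened event whose later record is rated less related will keep the earlier record's rating unless the investigator has revised that record. Protocol section 11.3.10 requires changes from the planned analysis to be described and justified in an amendment or the clinical trial report. SAP section 5 says that the SAP was prepared after review of the data, so this change must be marked as made at that stage.

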### **11.3.8.2 Vital Signs**

For vital signs (systolic and diastolic blood pressure, heart rate and temperature), the absolute value by visit and change from baseline (SV2) to each visit will be summarised.

Clinically significant abnormalities in the vital signs at baseline (SV2) and Week 4 will be presented. Any abnormalities at Week 4 that were not present at baseline will be highlighted.

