15. Any clinically significant abnormality following review of screening laboratory tests (blood and urine samples), physical examination or blood pressure/heart rate measurement performed at SV2.
16. Current participation in any other interventional clinical trial.
17. Previously treated with LEO 90100 in this trial.
18. Subjects who have received treatment with any non-marketed drug substance (i.e., an agent which has not yet been made available for clinical use following registration) within a month prior to SV1 or longer, if the class of substance required a longer wash-out as defined above (e.g., biological treatments).
19. In the opinion of the (sub)investigator, subjects or parent(s) or legal guardian known or suspected of being unlikely to comply with the Clinical Trial Protocol (e.g., alcoholism, drug dependency or psychotic state).

20. Females who are pregnant, or of child-bearing potential and wishing to become pregnant during the trial, or who are breast-feeding.
21. Females of child-bearing potential with positive pregnancy test at SV2.
22. Subject (or their partner) not using an adequate method of contraception according to national requirements.
23. Subjects who are dependant on the trial sponsor or investigator.
24. Subjects afraid of blood withdrawals.

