## 8 Trial Schedule and Assessments

### 8.1 Schedule of Trial Procedures

**Table 1: Schedule of Trial Procedures – Non-HPA Axis Cohort**

**Note:** Separate schedule of trial procedures for subjects in the HPA axis cohort below.

Visit	SV1 	SV2 	1	2	3	EW	FU 
Day	-28 to -7	-7 to -3	0	14 ± 2	28 ± 2	--	+ 14 ± 2
Informed consent	X						
Demographics	X						
Medical history and concurrent diagnoses	X						
Physical examination	X				X	X	
Height, weight and BSA 	X		X				
Inclusion/exclusion criteria	X	X	X				
Vital signs (blood pressure, heart rate, oral or ear temperature)		X	X	X	X	X	
25-hydroxy Vitamin D		X					
Haematology/biochemistry/urinalysis 		X			X	X	X 
Instructions for dietary calcium intake diary	X			X			
Review of dietary calcium		X			X	X	
Urine pregnancy test 		X			X	X	
Adverse events		X	X	X	X	X	X
Local safety and tolerability			X	X	X	X	
Concomitant medication	X	X	X	X	X	X	X
Physician's assessment of extent of psoriasis vulgaris		X	X		X	X	
Physician's assessment of extent of body psoriasis		X	X		X	X	
Physician's assessment of extent of scalp psoriasis		X	X		X	X	
Physician's global assessment of disease severity on the body		X	X	X	X	X	
Physician's global assessment of disease severity on the scalp		X	X	X	X	X	
Physician's assessment of the extent and severity of clinical signs of psoriasis vulgaris (for PASI)		X	X	X	X	X	
Subject's global assessment of disease severity on the body		X	X	X	X	X	
Subject's global assessment of disease severity on the scalp		X	X	X	X	X	
Subject's assessment of itch and itch-related sleep loss			X	X	X	X	
CDLQI 			X	X	X	X	
FDLQI 			X		X	X	
Dispensing of IP			X	X			
Return of IP				X	X	X	
IP Compliance				X	X	X	

- 1) There should be at least 4 days between SV1 and SV2 so dietary information (diary) can be collected.
- 2) Follow-up Visit 1 is only applicable for subjects who at the last on-treatment visit have an ongoing Serious Adverse Event of any causality or ongoing non-serious adverse event(s) classified as possibly/probably related to the investigational product and for subjects with albumin corrected serum calcium above reference range at the last on-treatment visit.
- 3) Body surface area (BSA) to be calculated using the Mosteller formula ([Appendix 9](#)).
- 4) Blood and spot urine samples should be collected at the end of treatment for subjects who are withdrawn from trial prior to Visit 3.

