### 8.4 Vital Signs

Vital signs must be assessed.

Recording of vital signs comprises:

- Heart rate (beats per minute), supine after 5 min rest
- Blood pressure, systolic and diastolic (mmHg), supine after 5 min rest
- Oral or ear temperature (location to be recorded in the subject's medical record)

The same arm will be used for all measurements. The arm (right or left) used for measurement will be recorded in the CRF.

Assessment of vital signs resulting in abnormal values will be repeated in order to exclude an erroneous assessment. Individual results will be classified as "normal", "abnormal with no clinical significance" or "abnormal with clinical significance".

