6.3.5 Other observations

PK evaluation

The PK evaluation will be presented in a bioanalytical report.

Plasma concentrations will be presented in the listing.

Vital signs

For systolic and diastolic blood pressure, heart rate and temperature, the absolute value by visit and change from baseline to each visit will be summarized

Clinically significant abnormalities in the vital signs at baseline and Week 4 will be presented. Any abnormalities at Week 4 that were not present at baseline will be presented in the listing.

The following approach will be used in case of repeated vital signs measurements:

- if an initial measurement was normal but the measurement was still repeated then the initial measurement will be presented in the tables
- if an initial measurement was abnormal and the measurement was repeated then the average of both measurements will be presented in the tables.

All measurements will be included in the listings (initial measurement and repeated measurements).

Baseline for vital signs is defined as last observation collected prior the first application of IMP (visit 1 and not screening visit 2 as written in the protocol).

Local Safety and Tolerability

Local safety and tolerability will be tabulated as described in the protocol.

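### New clinically significant vital-sign abnormalities at Visit 2 or early withdrawal are not flagged or counted, because the abnormality rule covers only baseline and Week 4

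*Protocol*

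**What the plan says.** The schedules for both cohorts (Protocol 8.1, Tables 1 and 2) have a row for "Vital signs (blood pressure, heart rate, oral or ear temperature") marked at SV2, Visits 1, 2 and 3 and early withdrawal. Protocol 8.4 grades the results without limiting this to particular visits: "Individual results will be classified as" normal, or as abnormal either without or with clinical significance.

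Protocol 11.3.8.2 treats the numbers and the grades differently. For the numbers, "the absolute value by visit and change from baseline (SV2) to each visit will be summarised". For the grades, "Clinically significant abnormalities in the vital signs at baseline (SV2) and Week 4 will be presented", and then "Any abnormalities at Week 4 that were not present at baseline will be highlighted".

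SAP 6.3.5 has the same restriction: "Clinically significant abnormalities in the vital signs at baseline and Week 4 will be presented". It declares one change, moving the vital-sign baseline from SV2 to Visit 1, and it puts new Week 4 abnormalities in a listing. SAP Appendix I plans Tables 3-66 to 3-73 (values and changes by visit) and Listing 8-5. It plans no table of clinically significant vital-sign abnormalities.

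**The concern.** The grade is the investigator's judgement that a reading matters, and it is recorded at two kinds of post-dose assessment that the abnormality rule leaves out. If a subject has a clinically significant reading at Visit 2 and a normal one at Visit 3, the rule shows nothing new. If a subject has one at early withdrawal, there is no Week 4 reading for the rule to pick up.

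Visit 2 deserves attention for a further reason. Under Protocol 6.1 (Treatment Period), subjects outside the HPA cohort may stop applying the product to lesions that have cleared at Visit 2, while remaining in the trial. For a subject who stops altogether and does not restart, Visit 2 is the on-treatment reading and Week 4 an off-treatment one. The rule then keeps the second and passes over the first.

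Safety is the primary objective, so the safety display should not miss graded findings when including them costs almost nothing.

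**Working it through.** The plan states no figure for this point, so the check sets the sections side by side.

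| Assessment | Measured and graded (8.1, 8.4) | In numeric by-visit summary | Under the abnormality rule | New ones singled out |
|---|---|---|---|---|
| SV2 | yes | yes | yes, as protocol baseline | not applicable |
| Visit 1 | yes | yes | yes, as SAP baseline | not applicable |
| Visit 2 | yes | yes | no | no |
| Visit 3 (Week 4) | yes | yes | yes | yes |
| Early withdrawal | yes | not stated | no | no |

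**Could another rule fill the two gaps?**

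- *End-of-treatment value.* Protocol 11.3.10 presents it for laboratory endpoints, efficacy and patient-reported outcomes. Vital signs are not named, and Tables 3-66 to 3-73 do not include it. An early-withdrawal reading therefore does not stand in for Week 4.
- *By-visit tables.* Protocol 11.3.10 includes minimum and maximum in continuous summaries, so an extreme Visit 2 value can be seen. It carries no grade and gives no count of subjects. Protocol 8.4 requires abnormal readings to be repeated, and SAP 6.3.5 then tabulates the average of the two, so the extreme shown may be milder than the first reading.
- *Listing 8-5.* It holds all measurements, including repeats. SAP 6.3.5 singles out only new Week 4 abnormalities.
- *Adverse events.* The general definition in Protocol Appendix 2 covers any unfavourable and unintended sign, so such a finding can be reported and tabulated. The explicit requirement to report a clinically significant abnormality as an adverse event (8.12.1 and Appendix 2) names laboratory findings only. The route exists but depends on the investigator.

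**Size, as far as the documents allow.**

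- *Early withdrawal.* The serum calcium row of SAP Table 2 has totals of 106 at screening and 103 after baseline. The second column is headed Visit 2, but laboratory tests are scheduled at SV2 and Visit 3, so I assume it is Week 4. Then (106 − 103)/106 = 2.8%, or about 3 subjects. This is a laboratory denominator used as a stand-in for vital-sign attendance.
- *Possible off-treatment Week 4 readings.* SAP Table 2 has 34 subjects in the 24-hour urine HPA rows and 72 in the non-HPA spot-urine row at screening (34 + 72 = 106). Up to 72 subjects were thus in the group allowed to stop; how many did is not given. For a subject who stopped at Visit 2, Week 4 comes 28 − 14 = 14 days later, or 10 to 18 days with the ±2-day windows.
- *Illustration only.* Take 103 subjects with both visits and a per-visit rate q of new clinically significant abnormalities. Week 4 alone is expected to show 103q subjects. If the visits are independent, either visit shows 103[1 − (1 − q)²].

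| q | Week 4 only | Visit 2 or Week 4 | Missed |
|---|---|---|---|
| 0.5% | 0.5 | 1.0 | 0.5 |
| 1% | 1.0 | 2.0 | 1.0 |
| 2% | 2.1 | 4.1 | 2.0 |

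If every Visit 2 abnormality persisted to Week 4, none would be missed. The documents give neither the rate nor the persistence, so the plausible loss runs from zero to a few subjects.

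**The case against.** The strongest reply is that this is a display preference for data already shown elsewhere. The by-visit tables include extremes, Listing 8-5 is complete, and a new finding that an investigator judges clinically significant fits the general adverse-event definition. The laboratory sentence in Appendix 2 adds to that definition and does not narrow it. Protocol 9.1 tells investigators to record changes they observe, and 9.4.6 makes clinically significant worsening of a medical condition reportable. An event that starts after first application is tabulated whatever the visit. All of this stands. A reader might infer that Visit 2 abnormalities vanish from the report, or that the adverse-event tables cannot show them; the documents support neither.

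It is also fair to say that Appendix I has no dedicated abnormality table for any visit, so Visit 2 is not being dropped from a planned table that includes Week 4. What remains is that the written rule names two time points and singles out one.

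Two other inferences go too far. Because one of the two scheduled post-dose visits lies outside the rule, a reader might conclude that half of the abnormalities are missed. A share of visits is not a share of abnormalities, and the documents give no vital-sign attendance. A reader might also think the baseline comparison empty because exclusion criterion 15 refers to any significant abnormality on "physical examination or blood pressure/heart rate measurement performed at SV2". That wording leaves out temperature and acts at SV2, whereas the SAP baseline is Visit 1.

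Finally, the Protocol Summary (Appendix 1) has blood pressure and temperature measured only at SV2 and Visit 3, which might seem to explain the restriction. It contradicts both schedules and the by-visit analysis, so it does not justify the rule; those passages need reconciling.

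**Conclusion.** The point holds as a low-cost improvement. As written, the rule in Protocol 11.3.8.2 and SAP 6.3.5 neither flags nor counts a new clinically significant vital-sign abnormality that is present at Visit 2 and gone by Week 4, or one found at early withdrawal. No other planned output counts such findings by grade. Local tolerability, by comparison, is tabulated at each visit (Protocol 11.3.8.3), and no reason is given for treating graded vital signs differently.

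The expected impact is small. Vital signs are neither a primary nor a secondary endpoint, early withdrawal concerns about 3 of 106 subjects if the Table 2 reading above is right, and SAP 6.3.3 reports no serious adverse events and no withdrawals due to an adverse event. Visit 2 is the main part of the point. The conclusion rests on the text of the rule and the schedules; the sizes rest on the stated assumptions, and the actual number of abnormalities is unknown.

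**What to change.** Change Protocol 11.3.8.2 and SAP 6.3.5 to present, for each vital sign, the number and percentage of subjects with a clinically significant abnormality at any assessment after first application (Visit 2, Visit 3 or early withdrawal) that was not present at the last pre-dose assessment, which is Visit 1 under the SAP. Add this as one table in SAP Appendix I beside Tables 3-66 to 3-73, and flag the same subjects in the vital-signs listing. The SAP was written after the data had been reviewed, so the addition should be declared as a change in the way Protocol 11.3.10 provides. The cost is one extra table and a listing flag, with no new data collection or grading.
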